## 5. Inclusion/Exclusion Criteria

### Inclusion Criteria:

Adults age 20-100 years old with degenerative changes of the shoulder joint (documented by radiographs) in patients planning total joint replacement with [name] (PI of this study) at Johns Hopkins Shoulder Service (Columbia, Odenton Clinic sites; HCGH/Bayview/JHH operative sites), with [name] at the University of Texas Sports Medicine and Shoulder Service, with [name] at MedStar St. Mary's Hospital Shoulder Service, and with [name] at William Beaumont Army Medical Center will be included. Patients who require revision surgeries, hemiarthroplasties, or who have chronic pain issues will be included.

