#### **4. Study Procedures**

- a. Study design, including the sequence and timing of study procedures (distinguish research procedures from those that are part of routine care).

Study Design: After the decision to proceed with shoulder replacement surgery, patients will be asked to participate in this prospective randomized clinical trial.

Study Groups:

- Group 1 will receive interscalene nerve block.
- Group 2 will receive liposomal bupivacaine with local bupivacaine for postoperative analgesia.

Study Procedures:

1. Before Surgery: The Informed Consent process will be completed prior to any data collection. Consent will be completed after explanation of each treatment group and the data to be collected. The following baseline data will be collection prior to surgery:

- Demographics (including age, sex, BMI, work status, living environment)
- Medical and Surgical History
- ASA Physical Status Classification
- Charlson Comorbidity Index Score
- Pain History and Medications
- VAS pain score

2. Randomization: Subjects will be randomized prior to surgery into one of the two perioperative analgesia groups. Randomization will be stratified by gender.

3. Surgery/Inpatient Stay:

- Group 1: Patients in the interscalene nerve block group will be given a single shot block in the preoperative area by a fellowship-trained anesthesiologist. The shot will contain a local anesthetic like 5% Ropivacaine (5 mg/1 mL) with a 44 millimeter 22 gauge needle with the patient in the supine position.
- Group 2: The surgeon at each site will be trained prior to enrollment on the correct way to perform Exparel injections intraoperatively. The surgeon will give patients in the liposomal bupivacaine group the periarticular injection

containing 266 mg of the drug in 40 mL injectable saline in the operating room; local 0.5% bupivacaine-epinephrine will also be used not to exceed dose limits.

- Surgical/Inpatient Data Collection:
  - Pre-op procedure time
  - Surgical time
  - PACU time
  - Admission/Discharge time and date
  - Estimated blood loss
  - Procedures performed
  - Inpatient pain medications administered
  - Patient VAS scores every 6 hours after surgery

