## 7. Study Statistics

- a. Primary outcome variable.

- VAS pain score at 24 hours postop.

- b. Secondary outcome variables.

- VAS scores at all other data points,

- Pain medication consumption (narcotics, NSAIDs, Tylenol)
- Opioid-induced side effects (nausea, vomiting, constipation)
- Length of hospital stay
- 30 day readmission rate.

- c. Statistical plan including sample size justification and interim data analysis.

A power analysis was performed to determine the sample size needed to determine noninferiority between groups with respect to VAS pain score. The minimal clinically important difference of VAS is 1.4 cm^13. The number was found to be 42 patients in each group, for a total n = 84. To ensure we reach this number, each of the 4 sites will aim to enroll 30 patients, to account for drop out.

The age of the two treatment groups will be compared using t-test. Sex distribution and the ASA scores of the groups will be compared using a chi-squared test and a Fisher exact test, respectively.

The median and interquartile range of the VAS scores at each of the time points measured will be tabulated by treatment group, and at each time point the difference between groups will be tested using non-parametric rank sum tests.

We will test the longitudinal trajectory of VAS scores over time, taking into account repeated measurements in the same patients using linear mixed model analysis. Treatment group, time period as a categorical variable, and the interaction between treatment and time period will be included as fixed effects, and patient ID will be included as the random effect. An initial omnibus test will be performed for all treatment and treatment by time interaction effects. If significant, the treatment by time interaction will be tested subsequently for each of the measurement periods.

The association of day of discharge (as a categorical variable) with treatment will be tested using the Fisher exact test.

- d. Early stopping rules.

We will monitor operative and post-operative complications including implant failures, nerve injuries, hematomas, and infections. We do not anticipate issues with these complications, as both techniques are in routine use in our current clinical practice. We did not find any differences in the complication rates in our retrospective cohort analysis.

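### The VAS analyses use no baseline covariate although a mixed population is enrolled and its pain history recorded: a minor, avoidable loss of precision, not a bias

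*Combined protocol and SAP*

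**What the plan says.** The inclusion criteria in section 5 are deliberately broad: "Patients who require revision surgeries, hemiarthroplasties, or who have chronic pain issues will be included".

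Section 4 lists "Pain History and Medications" among the data taken before surgery, together with a baseline VAS score. It lists "Procedures performed" under the surgical and inpatient data. On allocation it says only: "Randomization will be stratified by gender".

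Section 7a names the primary outcome as "VAS pain score at 24 hours postop". Section 7c then gives two VAS analyses:

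- Rank sum tests: "at each time point the difference between groups will be tested using non-parametric rank sum tests".
- A linear mixed model: "Treatment group, time period as a categorical variable, and the interaction between treatment and time period will be included as fixed effects". Beyond these terms it has a single random term, for the individual patient.

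No baseline covariate appears in either. The planned baseline comparisons cover age, sex and ASA only. Pain medication consumption is a secondary outcome in 7b, but 7c gives no test or model for it.

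**The concern.** The plan admits patients whose postoperative pain and opioid use may well differ from those of an uncomplicated primary replacement, and it collects the history that would identify many of them. It then leaves that information out of the comparison. Between-patient variation that a pre-specified covariate could explain stays in the error term, and the confidence interval is wider than it need be. That matters somewhat more here because 7c frames the sample size as a noninferiority question with 1.4 cm as the reference difference, and interval width bears directly on a noninferiority conclusion.

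The patient random effect does not fill the gap. It models correlation among repeated scores in one patient; it does not adjust the between-arm contrast for chronic pain or procedure type. Nor does the plan name baseline VAS as a covariate.

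**Working it through.** **Inputs from the documents.** 60 patients enrolled per arm and 15% dropout (section 4); 42 per arm required and a reference difference of 1.4 cm (section 7c). Evaluable per arm: 60 × (1 − 0.15) = 51.

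**The plan's own figure.** The 42 per arm can be neither confirmed nor refuted, because SD, alpha and power are not stated. Solving backwards with a true difference of zero, SD = 1.4 / [(z₁₋α + z_power) × √(2/42)]:

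- one-sided 0.025, 80% power: 1.4 / (2.802 × 0.218) = 2.29 cm
- one-sided 0.025, 90% power: 1.98 cm
- one-sided 0.05, 80% power: 2.58 cm
- one-sided 0.05, 90% power: 2.19 cm

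This supports 2.0-2.6 cm as a working range for the SD, and no more than that.

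**Assumptions, not in the documents.** Prevalence p of chronic pain or preoperative opioid use 20-40%; 24-hour VAS higher by d = 1-2 cm in these patients; total SD 2.0-2.6 cm.

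**Formulas.**
- Share of variance explained: R² = p(1 − p)d² / SD²
- Unadjusted 95% half-width: 1.96 × SD × √(2/51)
- Adjusted half-width: unadjusted × √(1 − R²)
- Equivalent unadjusted n per arm: 51 / (1 − R²)

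**Results.** The unadjusted half-width is 1.96 × 2.0 × 0.198 = 0.78 cm at SD 2.0, and 1.96 × 2.6 × 0.198 = 1.01 cm at SD 2.6.

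| SD (cm) | p | d (cm) | R² | Narrowing (cm) | Equivalent n per arm |
|---|---|---|---|---|---|
| 2.6 | 20% | 1 | 2.4% | 0.01 | 52 |
| 2.6 | 40% | 1 | 3.6% | 0.02 | 53 |
| 2.0 | 20% | 1 | 4.0% | 0.02 | 53 |
| 2.0 | 40% | 1 | 6.0% | 0.02 | 54 |
| 2.6 | 20% | 2 | 9.5% | 0.05 | 56 |
| 2.6 | 40% | 2 | 14.2% | 0.07 | 59 |
| 2.0 | 20% | 2 | 16.0% | 0.06 | 61 |
| 2.0 | 40% | 2 | 24.0% | 0.10 | 67 |

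The narrowing runs from 0.01 / 1.4 ≈ 1% to 0.10 / 1.4 ≈ 7% of the reference difference. These figures take the covariate's effect at 24 hours as fully captured by the model. A single coefficient shared by all time points would gain somewhat less if the effect changes over time.

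**The case against.** A reader might infer that a chance excess of chronic-pain patients in one arm would bias the result. The arithmetic looks impressive: with 51 per arm, the 95% limit for chance imbalance is 1.96 × √(2 × 0.2 × 0.8 / 51) = 15.5 percentage points at 20% prevalence and 19.0 points at 40%. With d of 1-2 cm that is a shift of 0.16-0.38 cm, or 11-27% of 1.4 cm. The documents do not support reading this as bias, or as a harm additional to the lost precision. Allocation is random, so the imbalance is itself the extra variance, and the unadjusted standard error already includes it. The narrowing in the table is the proper measure of what adjustment buys.

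The second objection is that enrolment already provides a cushion. Going from 42 to 51 per arm offsets an R² of up to 1 − 42/51 = 17.6%, which covers seven of the eight rows above. That stands as a reason to call the point minor. It depends on dropout staying at 15%, and it is unknown whether the planning SD already reflects a mixed population. A cushion is also no reason to forgo precision from data already in hand.

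Third, nothing in the documents shows how far these patients differ in pain, and no figure there supports a larger effect on opioid totals. This stands: the sizes above are assumptions, and no size is claimed for opioids.

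Fourth, adding covariates to the mixed model would leave the 24-hour rank sum test untouched, the procedure record is listed with data gathered at or after surgery, and there is no medication analysis to which covariates could be added. All three are correct and shape the fix. Which covariates to choose is partly judgement; baseline VAS and gender are also candidates.

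**Conclusion.** The point holds as a minor improvement in precision. The documents are clear that the population is mixed, that pain and medication history is collected before surgery, and that no VAS analysis uses it. The planned tests remain valid and nothing here corrects a bias. With 51 evaluable per arm and the assumed prevalence, shift and SD, adjustment removes about 2-24% of the variance and narrows a half-width of 0.78-1.01 cm by about 0.01-0.10 cm. Most of the grid lies in the lower part of the variance range; the top needs 40% prevalence, a 2 cm shift and an SD of 2.0 together. For medication consumption, the documents support only the statement that no analysis is specified.

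**What to change.** In section 7c:

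1. Add two pre-specified fixed effects to the VAS mixed model: a yes/no indicator of chronic pain or preoperative opioid use, defined in advance from the baseline record, and the planned procedure type as fixed before randomisation, with sparse categories collapsed. Use the planned procedure, not the one recorded at surgery.
2. State that the model's adjusted 24-hour treatment contrast, with its confidence interval, is the primary VAS comparison. Keep the rank sum test as supportive.
3. When an analysis of medication consumption is specified, include the same chronic pain or preoperative opioid covariate.

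Make no change to the randomisation strata or to eligibility. The cost is a few degrees of freedom, one definition written in advance, and making sure the planned procedure is noted before allocation. The covariates should be fixed before outcome data are seen, since adjustment chosen after an imbalance appears is open to challenge.

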### Exclusion Criteria:

Patients with an allergy to liposomal bupivacaine will be excluded. Patients with contraindications to the interscalene nerve block (preexisting neurologic defects, local anesthetic allergy, coagulopathy, contralateral phrenic nerve dysfunction, severe chronic obstructive pulmonary disease) will be excluded as these patients could not be randomized.

## 6. Drugs/ Substances/ Devices

- a. The rationale for choosing the drug and dose or for choosing the device to be used.

Drug and dosing used are the same as in the prior retrospective study.

- b. Justification and safety information if FDA approved drugs will be administered for non-FDA approved indications or if doses or routes of administration or participant populations are changed.

N/A

- c. Justification and safety information if non-FDA approved drugs without an IND will be administered.

N/A

## 7. Study Statistics

- a. Primary outcome variable.

- VAS pain score at 24 hours postop.

- b. Secondary outcome variables.

- VAS scores at all other data points,

- Pain medication consumption (narcotics, NSAIDs, Tylenol)
- Opioid-induced side effects (nausea, vomiting, constipation)
- Length of hospital stay
- 30 day readmission rate.

- c. Statistical plan including sample size justification and interim data analysis.

A power analysis was performed to determine the sample size needed to determine noninferiority between groups with respect to VAS pain score. The minimal clinically important difference of VAS is 1.4 cm^13. The number was found to be 42 patients in each group, for a total n = 84. To ensure we reach this number, each of the 4 sites will aim to enroll 30 patients, to account for drop out.

The age of the two treatment groups will be compared using t-test. Sex distribution and the ASA scores of the groups will be compared using a chi-squared test and a Fisher exact test, respectively.

The median and interquartile range of the VAS scores at each of the time points measured will be tabulated by treatment group, and at each time point the difference between groups will be tested using non-parametric rank sum tests.

We will test the longitudinal trajectory of VAS scores over time, taking into account repeated measurements in the same patients using linear mixed model analysis. Treatment group, time period as a categorical variable, and the interaction between treatment and time period will be included as fixed effects, and patient ID will be included as the random effect. An initial omnibus test will be performed for all treatment and treatment by time interaction effects. If significant, the treatment by time interaction will be tested subsequently for each of the measurement periods.

The association of day of discharge (as a categorical variable) with treatment will be tested using the Fisher exact test.

- d. Early stopping rules.

We will monitor operative and post-operative complications including implant failures, nerve injuries, hematomas, and infections. We do not anticipate issues with these complications, as both techniques are in routine use in our current clinical practice. We did not find any differences in the complication rates in our retrospective cohort analysis.

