**1. Abstract**

- a. Provide no more than a one page research abstract briefly stating the problem, the research hypothesis, and the importance of the research.

The incidence of shoulder replacements is quickly rising with the growing elderly population and new technologies, such as the reverse shoulder replacement. At this time, there are 53,000 shoulder replacements performed annually according to the Agency for Healthcare Research and Quality. The interscalene (IS) brachial plexus nerve block is considered the gold standard for shoulder anesthesia. While complications for IS nerve blocks are rare, they include chronic neurologic complications and substantial respiratory, cardiovascular, and central nervous system events. Femoral nerve blocks used in total knee arthroplasty are associated with complications such as insomnia, antalgic ambulation, and difficulty with rehabilitation, and increased incidence of falls.

A new approach to postoperative analgesia is the periarticular injection method, by which the surgeon administers local infiltration analgesia without the help of an anesthesiologist. Recent literature has shown that the liposomal bupivacaine (Exparel®) injection provides better pain control, shortens hospital stays, and decreases costs for total knee and hip arthroplasties compared to the gold standard nerve block methods. Broome et. al found that total knee arthroplasty patients who had a liposomal bupivacaine injection saved an average of \$600 compared to those who received a femoral nerve block. This translated to a savings of approximately one million dollars per year at their hospital alone. Eliminating the costs associated with interscalene nerve block administration in shoulder replacements could allow for significant cost-savings to our healthcare system.

Currently, no published literature exists directly comparing liposomal bupivacaine and interscalene (IS) nerve blocks in shoulder replacements. This study would provide a direct comparison of available postoperative analgesia techniques for shoulder arthroplasty. The results of this work will demonstrate whether the liposomal bupivacaine injection technique results in the same postoperative pain compared to the typical interscalene nerve block method.

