There were 21 patients in the IS nerve block group and 37 patients in the liposomal bupivacaine group who met all inclusion criteria. Baseline demographic data for age ( $p=0.53$ ), sex ( $p=0.71$ ), BMI ( $p=0.09$ ), and ASA ( $p=0.33$ ) did not differ between groups. The primary outcome measure, NRS pain score, showed no significant differences between groups at 0–1 hours after surgery ( $P = .99$ ) or 8–14 hours after surgery ( $P = .208$ ). At 18–24 hours after surgery, the liposomal bupivacaine group had a lower mean NRS score than the ISNB group ( $P = .001$ ). This was statistically significant when taking repeated measures of variance into account (Fig. 1). Mean NRS score was also lower for the liposomal bupivacaine group at 27–36 hours after surgery ( $P = .029$ ). This was not statistically significant when repeated measures of variance were considered (Table II).

There was no difference in the amount of intravenous acetaminophen given during the hospital stay between groups. There was no statistically significant difference in opioid consumption on postoperative day 1 in the hospital ( $P = .59$ ). However, there were significant differences between groups on postoperative days 2 and 3 (Fig. 2). On postoperative day 2, the ISNB group required significantly more opioids (112 mg) than the liposomal bupivacaine group (37 mg) ( $P = .001$ ). The ISNB group also required significantly more opioids (25 mg) on postoperative day 3 than the liposomal bupivacaine group (5 mg) ( $P = .002$ ).

Sixteen of 37 patients in the liposomal bupivacaine group and 2 of 21 in the ISNB group (Table III) were discharged on the day after surgery. The mean LOS was  $46 \pm 20$  hours for the liposomal bupivacaine group and  $57 \text{ hours} \pm 14$  hours for the ISNB group ( $P = .012$ ).

There were no major cardiac or respiratory events in either group. No long-term paresthesias or neuropathies were noted. There were no readmissions for either group.

Liposomal bupivacaine injections may provide better pain control 18-24 hours after surgery and shorten hospital stays after shoulder arthroplasty compared to interscalene nerve blocks as a means of postoperative pain control. Based on these results, larger analytic studies including randomized trials should be performed to explore the potential benefits of liposomal bupivacaine injections for pain control after shoulder arthroplasty.

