#### 4. After Discharge:

- Patients will record the following information after discharge up until 96 hours from their surgery:
  - VAS scores every 6 hours
  - Pain medication consumption (dosages, times)
  - Opioid-related side effects
  - Level of satisfaction with pain management
- Study staff may conduct reminder phone calls to ensure patients complete outpatient data collection. The outcome assessor will be blinded to the treatment group.
- Patients will record their VAS pain scores again at their 1st postop appointment, which typically occurs 10-18 days after surgery.

Sample Size: There will be 60 patients in each group, for a total study population of n = 120.

Study Locations: This will be a multi-center study. The sample size will enroll 120 (to account for 15% drop out rate) patients total, with approximately 30 patients enrolled at each site. The other participating sites are as follows:

[name]  
Sports Medicine and Shoulder Service  
University of Texas, Southwestern Medical Center  
[name]  
[name]

[name]  
MedStar St. Mary's Hospital  
[name]  
[name]

[name]  
William Beaumont Army Medical Center  
[name]  
[name]

**Aim #2:** Determine the length of stay of liposomal bupivacaine compared to interscalene nerve block in patients undergoing total shoulder arthroplasty and calculate costs associated with any differentials.

- b. Study duration and number of study visits required of research participants.

Patients will be enrolled in this study for 2 weeks after their surgical date. This time frame will include their hospital stay and include their time at home after discharge up until 96 hours after their surgery, and their 2-week postop appointment data. If patients are not scheduled for their postop appointment within 10-18 days after surgery (which is standard clinical practice), the study team will call the patient to obtain their pain score and medication data. Patient names will be stored in a password-protected database for 30 days after discharge to calculate 30-day readmission rates.

Routine patient follow up is typically at 3, 6, and 12 months for the first year. Pain data and patient reported outcomes are collected at these visits as routine clinical care. Patients routinely complete the ASES and EQ-5D questionnaires at their 12 month follow up appointment.

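### The question about the same postoperative pain rests on VAS at 24 h alone; earlier scores are tested only for a difference, which cannot show that early pain is no worse

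*Combined protocol and SAP*

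**What the plan says.** The abstract (section 1) puts the question as "whether the liposomal bupivacaine injection technique results in the same postoperative pain compared to the typical interscalene nerve block method". It names no hour or period.

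Section 7a gives one primary outcome, "VAS pain score at 24 hours postop". Section 7b makes all other VAS scores secondary. Section 4 collects "Patient VAS scores every 6 hours after surgery", and patients continue the six-hourly record at home until 96 h, so readings at 6, 12 and 18 h should exist for each patient.

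Section 7c sizes the trial to "determine the sample size needed to determine noninferiority between groups with respect to VAS pain score". It adds that "The minimal clinically important difference of VAS is 1.4 cm" and reports the result: "The number was found to be 42 patients in each group, for a total n = 84". The analysis text then gives medians and interquartile ranges by arm, a rank sum test at each time point, and a mixed model with treatment, time and their interaction. Period-by-period tests in that model follow only a significant omnibus test.

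The pilot cohort in section 3 (21 block, 37 liposomal bupivacaine) found no significant difference at 0–1 h (P = .99) or 8–14 h (P = .208). "At 18–24 hours after surgery, the liposomal bupivacaine group had a lower mean NRS score than the ISNB group" (P = .001), and this held in the repeated-measures analysis. The 27–36 h difference (P = .029) did not.

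**The concern.** For a claim of no worse pain, the time point decides what is tested. The comparator is a single injection given before surgery, and the pilot P values differ by window, so the arms may well differ in time course. A favourable result at 24 h would then say little about the first 12 h.

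The secondary analyses do not close this gap, because they ask whether the arms differ. A non-significant test at 6 h or 12 h is compatible with no difference and also with a deficit of clinical size, and the plan asks for no interval that would separate the two. Nothing in section 7 makes the wording of the conclusion depend on those hours. The risk is a report that states the abstract's broad conclusion on the strength of one time point.

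**Working it through.** **Inputs.** From the documents: 1.4 cm, 42 per group (84 in total), 60 per group enrolled, 15% dropout, and the pilot group sizes and P values. Not in the documents, so assumed: 1.4 cm serves as the non-inferiority margin, one-sided alpha is 0.025 unless stated, VAS SD is 2–3 cm, and the correlation between time points is 0.3–0.7. Differences are liposomal bupivacaine minus block, so positive means worse.

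**1. The plan's own figure.** With n = 2·SD²·(z₁₋α + z_power)²/1.4² and a true difference of 0, the figure of 42 cannot be reproduced, because SD, alpha and power are not stated. Solving for SD gives 1.4·√21/(z₁₋α + z_power):

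| One-sided alpha | Power | Implied SD (cm) |
|---|---|---|
| 0.025 | 80% | 6.416/2.802 = 2.29 |
| 0.025 | 90% | 6.416/3.242 = 1.98 |
| 0.05 | 80% | 6.416/2.486 = 2.58 |
| 0.05 | 90% | 6.416/2.926 = 2.19 |

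Enrolment covers the target: 120 × 0.85 = 102, or 51 per arm.

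**2. How strongly the time point matters.** The chance of showing non-inferiority is Φ((1.4 − δ)/(SD·√(2/42)) − 1.96). With SD 2.29 the standard error is 0.50 cm:

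| True difference δ (cm) | −1.0 | −0.5 | 0 | +0.5 | +1.0 |
|---|---|---|---|---|---|
| Chance | 99.8% | 96.7% | 80% | 44% | 12% |

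If the arms differ over time, the choice of hour largely determines the answer.

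**3. What the pilot leaves open early.** The pilot test is not named. Treating each P value as a two-sample t-test on 56 df, the standardised difference is t·√(1/21 + 1/37) = t × 0.273.

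- 18–24 h: 3.47 × 0.273 = 0.95 SD in favour of liposomal bupivacaine.
- 8–14 h: 1.27 × 0.273 = 0.35 SD, direction not given. If it went against liposomal bupivacaine, the upper 95% limit is 0.35 + 2.00 × 0.273 = 0.90 SD, or 1.8–2.7 cm at SD 2–3.
- 0–1 h: about 0.003 SD, upper limit 0.55 SD, or 1.1–1.65 cm.

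The early point estimates are below 1.4 cm, but the early results do not rule out 1.4 cm.

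**4. What the planned early tests can miss.** Power of a two-sided 5% rank sum test, by normal approximation with relative efficiency 0.955, is Φ(δ/(SD·√(2/(0.955·n))) − 1.96). For δ = 1.4 cm and n = 42:

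- SD 2: Φ(1.4/0.447 − 1.96) = 88%, so 12% missed.
- SD 3: Φ(1.4/0.670 − 1.96) = 55%, so 45% missed.

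With 51 per arm the same formula gives 7% and 37% missed.

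**5. Cost of the broader claim.** Suppose non-inferiority must hold at 24 h and at two earlier times, with no alpha split, a true difference of 0 at each, SD 2.29 and equal correlation of 0.3–0.7. Joint power from the multivariate normal distribution is 57–66% at 42 per arm and 70–76% at 51. Reaching 80% needs 56–61 evaluable patients per arm.

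**The case against.** The best defence is that the early hours are already covered: VAS is recorded every 6 h, each time point has its own rank sum test, and the mixed model tests treatment by time. A large early deficit would very probably show. By the formula in step 4, with 42 per arm and SD 2–3 cm, +2.5 cm at 6 h would be detected with 96% to over 99% power, and +1.5 cm at 12 h with 61–92%. This stands. A reader might infer that the earlier hours go untested, and that would be wrong. What remains is the smaller deficit near 1.4 cm, and the fact that no planned result can positively support the statement that early pain is no worse.

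Second, the plan sets no non-inferiority rule that favours 24 h over other times. Non-inferiority appears only in the sizing sentence, and 24 h gets the same rank sum test as 6 h. This also stands. It is a separate gap, and it leaves the broad claim no better supported.

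Third, a reader might infer that the 24 h result is close to settled in advance. The documents do not support that. The 0.95 SD in step 3 comes from an unnamed test in a single-surgeon, non-randomised, retrospective cohort that used NRS, and confirming such a result in a randomised trial is reasonable.

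**Conclusion.** The point holds as a mismatch of scope. An open-ended question rests on one 24 h score, and the earlier scores are tested in a way that cannot establish that pain is no worse. At 42 per arm the planned early test misses a true 1.4 cm deficit about 12–45% of the time. That range rests on an assumed SD of 2–3 cm and a normal approximation, and reading 1.4 cm as the margin is also an assumption.

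Two stronger readings should be resisted. A reader might infer that liposomal bupivacaine gives worse early pain. The pilot does not show this: both early comparisons were non-significant and their direction is not given. A reader might also infer that 24 h was chosen to favour liposomal bupivacaine. The plan gives no reason for the choice, so nothing about intent follows. This is a cheap improvement to the plan and not a fault that invalidates the primary.

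**What to change.** Keep VAS at 24 h as the primary outcome and word its conclusion as pain at 24 h, in sections 1 and 7.

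From the mixed model already planned, report the between-group difference with its confidence interval at 6 h, at 12 h, and for the time-averaged VAS over 6–24 h, whatever the omnibus test shows. Read each against the 1.4 cm difference. State in advance that the broad claim of the same postoperative pain will not be made if the interval for the 6–24 h average, or either early interval, includes a 1.4 cm deficit for liposomal bupivacaine. Settle this before any comparison by arm is seen.

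The cost is some wording and three estimates from data already collected. The primary and the sample size are unchanged, and the 24 h claim keeps its power. The broad claim has less power: the similar three-time-point requirement in step 5 reaches only about 57–66% at 42 per arm, if 42 was sized for 80% at one-sided 0.025 with a true difference of 0. Requiring all the intervals jointly is the debatable part. A sponsor who finds it too strict can still report the intervals and confine the conclusion to 24 h.
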